**Title: Impact of a low-carbohydrate versus low-fat breakfast on blood glucose control in type 2 diabetes**

**Research Question:** Does a low-carbohydrate breakfast impact blood glucose levels in people with type 2 diabetes?

**Objectives**

- 1) To determine whether a low-carb high-fat (LCHF) breakfast, compared to a standard control low-fat (CTL) breakfast impacts haemoglobin A1c (HbA1c; the clinical marker of glucose control) in individuals with T2D;
- 2) To evaluate if compared to a low-fat breakfast, a low-carb high-fat breakfast influences satiety and daily caloric intake in individuals with T2D;
- 3) To determine whether a low-carb high-fat breakfast, compared to a standard control low-fat breakfast alters body weight in individuals with T2D;
- 4) To determine whether a low-carb high-fat breakfast alters glucose levels, blood lipid profile and inflammation biomarkers compared to a low-fat breakfast in individuals with T2D;
- 5) To verify if compared to a low-fat breakfast, a low-carb high-fat breakfast raises lutein levels and improves cognition in individuals with T2D.

**Hypothesis:**

- a) A low-carb high-fat breakfast, compared to a standard control low-fat breakfast will reduce HbA1c levels
- b) When compared to a low-fat breakfast, low-carb high-fat breakfast will improve satiety and lower daily caloric intake.
- c) Compared to a low-fat breakfast, a low-carb high-fat breakfast will lower body weight in individuals with T2D;
- d) A low-carb high-fat breakfast will improve glucose levels, blood lipid profile and inflammation biomarkers compared to a low-fat breakfast in individuals with T2D;
- e) Compared to a low-fat breakfast, a low-carb high-fat breakfast will raise lutein levels and consequently improve cognition functions.

**Background Information**

Diabetes is a rapidly growing public health problem worldwide. Among adults aged 20–79 years in 2017 there was an estimated 425 million cases of diabetes. Over 90% of these have type 2 diabetes (T2D); a chronic, progressive condition that is characterized by profound insulin resistance and pancreatic beta-cell dysfunction that leads to elevated blood glucose levels [1]. Chronically elevated blood glucose

(i.e., hyperglycemia) contributes to the devastating complications of T2D, including cardiovascular disease, retinopathy, and neuropathy [2].

More than 100 million U.S. adults are now living with diabetes or prediabetes, according to a report released by the Centers for Disease Control and Prevention (CDC) [3]. In 2015, 30.3 million Americans, or 9.4% of the population, had diabetes. Another 84.1 million have prediabetes, a condition that if not treated often leads to type 2 diabetes within five years. Diabetes was the seventh leading cause of death in the U.S. in 2015. The total estimated cost of diagnosed diabetes in 2017 is \$327 billion, including \$237 billion in direct medical costs and \$90 billion in reduced productivity [3]. Clearly, strategies to improve glucose control and reduce the burden of T2D are attractive from a quality of life and economic standpoint.

In T2D, consuming carbohydrates results in a rapid and large increase in blood glucose. Accumulating evidence indicates that these postprandial “hyperglycemic spikes” are particularly important in driving the pathophysiology of diabetes complications. Postprandial hyperglycemia is an independent risk factor for cardiovascular disease and mortality [4] and lowering postprandial glucose spikes can reduce the risk of cardiovascular disease [5]. The highest hyperglycemic spike often occurs after breakfast, leading to the largest excursion of the day and thus breakfast is a crucial barrier preventing good glycemic control [6]. Lowering post-breakfast hyperglycemia therefore represents a key treatment opportunity for people with T2D.

Although we are unaware of any long-term (i.e. weeks/months) low-carbohydrate egg-based breakfast trials, previous studies have supported possible benefits of manipulating breakfast composition in order to improve blood glucose control and other health outcomes relevant to people with, or at risk for, T2D. Pedersen et al. [7] confirmed that in T2D, excluding carbohydrate from the first meal of the day could blunt the large breakfast glucose spike. Park et al. [8] showed that a high-protein breakfast lowers postprandial glucose concentrations at this meal and does not magnify the glucose response to the second meal, suggesting that adding protein to breakfast could be a therapeutic option for T2D. Over the longer-term, consuming a “big breakfast” containing higher fat and protein that provided 33% total daily energy over 3 months led to a significant reduction in HbA1c (the main clinical marker of glucose control that reflects average blood glucose levels over the previous 90-120 days) when compared to a small breakfast providing 12.5% daily energy [9]. Thus, previous research suggests that manipulating breakfast composition can have potential benefits for people with T2D.

Targeting the meal that leads to the largest glucose spike may be a simple, feasible strategy to improve glycemic control and reduce risk for future diabetes

complications. One strategy to eliminate this large hyperglycemic excursion is to consume an LCHF breakfast. Epidemiological studies report that the routine consumption of a LCHF breakfast could be beneficial for reducing the risk of T2D, cardiovascular disease, and other chronic diseases [10]. Recent experimental work from our lab published in the *American Journal of Clinical Nutrition* [11] shows a 74% reduction in 24-hour postprandial hyperglycemia with a LC breakfast (egg and cheese omelet) when compared to a standard low-fat breakfast (oatmeal with berries) in people with T2D. Consuming a low-carbohydrate high-fat breakfast could be a simple strategy to prevent the largest post-breakfast glucose spike and improve overall glucose control in T2D.

The potential benefits of a low-carbohydrate breakfast compliments previous research examining the impact of high-protein breakfasts. It has been demonstrated that the daily consumption of a high-protein rather than a high-carbohydrate breakfast prevented the gain in body fat, and caused reductions in daily hunger and daily food intake [9] [12] [13] [14] [15]. Indeed, in our recent study [11] we saw that consuming the LC breakfast (which was high in protein) led to lower feelings of hunger and desire to eat sweet “junk” foods later in the day.

Low-carb high protein breakfast are usually composed of eggs and bacon. Eggs contain a variety of essential nutrients that can impact human health. Egg yolks contain various antioxidant carotenoids. Among them, lutein and zeaxanthin are the only two that cross the blood-retina barrier to form macular pigment in the eye, and lutein is the dominant carotenoid in human brain tissue. In people with T2D, it is important to minimize progressive complications of the disease including cognitive impairment, macular degeneration and retinopathy. Lutein is increasingly recognized as having a role in cognitive function. The possibility of a low-carb high-fat breakfast with eggs having nutritional benefits that advance beyond regular metabolic control in T2D to influence the brain and eye is intriguing. [16] [17] [16] [17]

Taken together, our recently published work on improved glycemic control and reduced hunger with a low-carbohydrate breakfast in T2D patients [11] coupled with studies showing that high-protein breakfasts can have health benefits in T2D, provide strong rationale for a properly powered longer-term randomized controlled trial (RCT) to determine if regular consumption of a LCHF breakfast can lead to clinically important improvements in glycemic control and health markers in individuals with T2D. **We hypothesize that consuming a LCHF breakfast will improve blood glucose control, increase satiety and improve body composition, as well as cognitive function in people with T2D.** This

information will provide high quality scientific evidence for the potential health benefits of reducing carbohydrates at breakfast as a dietary strategy for managing T2D. The proposed RCT will significantly advance the existing evidence that has shown contribution of a LCHF consumption in improving body composition in T2D [15] by strategically incorporating a low-carbohydrate high-fat breakfast to test whether it can lower HbA1c, the key clinical treatment outcome in T2D. The findings will be easy-to-implement and could help solidify LCHF as the ideal breakfast option for people with T2D.

## Research Method

Eighty-two (N=82) individuals between University of British Columbia and University of Wollongong, Australia with physician diagnosed T2D (HbA1c < 8.5%), between the ages of 20-79 years, with a BMI above 25 kg/m^2 will be recruited through online social media and newspaper advertising. REACH BC and Trialfacts will assist with recruitment. REACH BC is an initiative of BC's health authorities and partner universities bridging the gap between the public and researchers. Trialfacts combines extensive marketing and advertising expertise with in-depth clinical trial experience to create effective marketing solutions. We have a partnership with the Kelowna Diabetes Program to assist recruiting from >6500 well-monitored T2D patients in our region.

**Inclusion criteria** will be: i) physician-diagnosed T2D of  $\geq 1$  year; ii) current HbA1c of <8.5%; iii) BMI: higher than 25kg/m^2; iv) blood pressure of <160/99 mm Hg assessed according to guidelines; v) non-smoking; vi) not on hormone replacement therapy, corticosteroids, or anti-inflammatory medications; and vii) 20–79 years old. **Exclusion criteria will include:** i) Use of exogenous insulin; ii) taking more than 2 glucose lowering medications; iii) ongoing medical treatment for diseases such as cancer, auto-immune or inflammatory disease, liver or kidney disorders; iv) allergy, intolerance or aversion to eggs or any other dietary restrictions (e.g., vegan, breakfast skipping) that will prevent them from following the standardized study diets; v) being unable to follow remote guidance by internet or smartphone; vi) being unable to follow the controlled diet instructions;.

Based on our previous studies ~55% of males and ~70% of females with T2D who volunteer will meet these eligibility criteria so we anticipate no recruitment issues. We will allow statins and anti-hypertensive medications if on a stable dose for 3 months because the majority of T2D patients are on at least one of these medications; excluding them would leave a small pool for recruitment and limit the generalizability of our findings.

A 3-month parallel-group randomized controlled trial is proposed. Eligible participants will be randomized to either the Low-carb High-fat breakfast (LCHF, n=41) or a low-fat “standard care” control breakfast (CTL, n=41), to be consumed daily for a period of 3 months.

Due to COVID-19 breakout, this study is proposed to be done remotely since participants belong to risk group and will probably maintain in quarantine for unpredictable time. Information and guidance for the trial will be done by email, telephone calls and text messages. RedCap-UBC will be used to manage information and deliver questionnaires.

Each group will be provided with a menu of 8 LCHF breakfasts or 8 CTL breakfasts from which to choose each morning. Breakfast options (designed by [name], Registered Dietitian) will be controlled in macronutrient content and calories (~400-500 kcal), but allow for personal preference and autonomy to promote adherence. Instruction will be given for digital recording of breakfast by a RedCap-UBC link sent by email. Participants will also be guided to register three 3-day food records (2 weekdays and 1 weekend day) at weeks 1, 6 and 12 of the trial using a diet logbook provided. Reminders to complete the 3-day food records and app will be given by telephone call, text messages and/or emails based on participant preference. We have used this approach successfully in several recent and ongoing trials [18] [19].

The Godin Leisure-Time Exercise Questionnaire will allow the assessment of self-reported leisure---time physical activity. The individual is asked to complete a self-explanatory, brief four-item query of usual leisure-time exercise habits at weeks 1, 6 and 12 of the trial.

Participants will complete 100 mm Visual Analog Scales (VAS) to measure self-reported hunger, fullness before each meal (breakfast, lunch and dinner) at weeks 1, 6 and 12 of the trial.

A cognition test will be performed at weeks 0, 6 and 12 by an online link provided to participant to be answered at home.

Before and after the 3-month intervention, an 8-10 hour fasting blood sample will be obtained. For the primary outcome, HbA1c participants will be asked results from a recent exam (less than 1 month old). If results are not recent, participants will be asked to go to a local laboratory for a new test. Participants with high levels of A1c (>8.5%) during screening will be notified via email and not eligible for the study. Secondary outcomes of fasting plasma glucose, insulin, blood lipid profile (triglycerides, total, HDL, and LDL cholesterol), carotenoids (lutein and zeaxanthin) and inflammation (high-sensitivity C-reactive protein [CRP] will be measured by a dried blood spot test. Dried blood spot is a form of collection where patients place blood drops on a filter card after a finger prick with a lancet. Once dry, blood spot cards are extremely stable for shipment and storage, and the dried blood format offers excellent correlation with serum tests. It offers distinct advantages because it eliminates the need for a blood draw and translocation – reducing patients burden.

A CGM device (Abbott FreeStyle Libre) will be inserted to participants' upper arm in order to collect continuous glucose readings during the first and last 14 days of the trial. CGM will serve to confirm that the LCHF meal lowers the post-breakfast

glucose spike and will provide details on daily postprandial hyperglycemia to be used in analyses of overall glucose control (24 h average, post-meal areas under the curve [AUC], and glycemic variability).

Self-reported weight and height will be registered at the beginning and end of the study.

**Study Timeline:**

1. Baseline contact
2. Day 0
3. Day 1
4. Day 7
5. Day 14
6. Day 21
7. Day 42
8. Day 84 – End of study

**Timeline:**

**Baseline Contact**

Participants will be recruited by email, online recruitment (including REACH BC and Trialfacts) or telephone call. Screening will be confirmed by filling out a Health Screening form and signing an electronic Consent form through a RedCap-UBC link. The postdoctoral fellow research lead ([name]) will ensure that the subjects understand the details of the study and consent form. After confirmation, participants will receive a study kit at their homes containing the following:

- Study Welcoming, Instructions and Responsibilities
- 2 Dry blood spot kit (beginning and end of study)
- Recipe book
- Controlled Glucose Monitor (CGM) Reader and sensor
- Food coupons and gift card

**Instructions will consist of:**

- A schedule and timeline of the study with participants' responsibilities;
- Instructions on Diet Habit Survey;
- A menu and preparation of 8 LCHF breakfasts or 8 CTL breakfasts recipes from which to choose each morning;
- How to send digital recording of breakfast by RedCap link;

- Guidance in registering three 3-day food records (2 weekdays and 1 weekend day) at weeks 1, 6 and 12 of the trial using an online diet logbook;
- How to answer questionnaires for self-reported hunger and fullness to be completed before each meal (breakfast, lunch and dinner) and a physical activity questionnaire (GODIN) at weeks 1, 6 and 12;
- How to complete the cognition test at day 0, day 42 and day 84;
- Blood collection instructions with link to explanatory video.

### **Day 0**

- ✓ Diet Habit Survey;
- ✓ TPB questionnaire;
- ✓ Baseline Cognition test;
- ✓ HbA1c results: participants should have a recent (less than 1 month from study start) HbA1c test or head to local lab for testing.

Diet Habit Survey will be answered by a link sent to participants through RedCap-UBC.

Cognition test will be sent as a link to be answered in a quiet room. Tests will last approximately 10 minutes.

### **Day 1**

- ✓ Blood sample collection
- ✓ Insert CGM 1

Blood drops will be collected by participants after having fasted overnight (8-10 h) and refrain from taking any medications on the morning to measure the primary outcome of HbA1c and associated secondary outcomes measures of fasting plasma glucose, insulin, blood lipid profile and inflammation. Envelope will be then sent to research team by mail.

CGM instructions will also be sent and a Zoom meeting can be scheduled to help participants with insertion of device.

### **Day 7**

- ✓ Self-reported Hunger and Fullness Questionnaire
- ✓ GODIN Physical Activity Questionnaire
- ✓ Diet Food log

### **Day 14**

- ✓ Remove CGM 1 and send by mail

### **Day 21 – Follow-up**

Research team will contact participants to follow-up on study and verify compliance to breakfast recipes as well as provide new ideas and guidance on possible issues.

**Day 42**

[figure not shown]
- ✓ Self-reported Hunger and Fullness Questionnaire
- ✓ GODIN Physical Activity Questionnaire
- ✓ Cognition Test
- ✓ Food log

**Day 70**

- ✓ Insert CGM 2

**Day 84**

- ✓ Self-reported Hunger and Fullness Questionnaire
- ✓ GODIN Physical Activity Questionnaire
- ✓ Cognition Test
- ✓ Food log
- ✓ TPB questionnaire
- ✓ Provide self-reported weight.
- ✓ Blood sample collection. Blood drops will be collected by participants after having fasted overnight (8-10 h) and refrain from taking any medications on the morning to measure the primary outcome of HbA1c and associated secondary outcomes measures of fasting plasma glucose, insulin, blood lipid profile and inflammation. Envelope will be then sent to research team by mail.
- ✓ Remove CGM 2 and send by mail.
- ✓ Cognition test. Cognition test will be sent as a link to be answered in a quiet room. Tests will last approximately 10 minutes.
- ✓ End of study Survey
- ✓ HbA1c results: participants should have a recent (less than 1 week from study end date) HbA1c test or head to local lab for testing.

## Statistical Analysis

This study will be reported according to the CONSORT 2010 statement for RCTs. Data will be analyzed on an intention-to-treat basis. Descriptive statistics (means, SD, and frequencies) will be calculated. Histograms and Q-Q plots of residuals will be used to identify any outliers and to test for normality. The primary outcome of HbA1c will be analyzed by linear mixed effects regression to assess differences between groups, with age and sex included in the model. Secondary outcomes will be analyzed similarly. Data with skewed distributions will be log-transformed prior to statistical testing or non-linear mixed effects regression will be performed. All participants will be included in the intention-to-treat analyses and missing data will not be imputed, per contemporary guidelines with use of linear mixed models.

## Sample size

We used a previous breakfast intervention in T2D along with our recently published one-day egg-based LC breakfast trial to calculate sample size for this RCT. Rabinovitz et al. [9] compared a “big breakfast” containing higher fat and protein providing 33% total daily energy to a small breakfast providing 12.5% daily energy over 3 months in a similar sample of participants with T2D using a similar parallel-group design. They reported an absolute reduction in HbA1c% of 0.46%. This is similar to the magnitude of change observed in a recent study by Nichols et al. [20] who reported an average HbA1c reduction of 0.45% in response to metformin, the standard prescribed medication for people newly diagnosed with T2D. For this reason, it is reasonable to use the study published by Rabinovitz et al. to estimate a clinically relevant effect size in our sample size calculation. A medium effect size (Cohen’s  $d = 0.46$ ) was calculated from the Rabinovitz study. In agreement, for our

recent one-day study examining an egg-based LC breakfast [11], the effect size (Cohen's d) for improvements in CGM-derived glucose control variables (including AUC, iAUC, glycemic variability, and mean) ranged from  $d = 0.48-1.2$ .

Taking a conservative approach, we used an effect size of  $d = 0.4$  in the sample size calculation. The total sample size necessary to detect a between-within interaction using repeated measures ANOVA with an effect size of  $d = 0.4$  (which corresponds to an ANOVA effect size  $f = 0.2$ ) with 90% power and 5% type 1 error with a conservative correlation among repeated measures of  $r=0.5$  is 68 ( $n=34$  per group, calculated using G\*Power v3.1.9.2). To account for a 20% dropout rate [9] we will recruit a sample size of  $n=41$  per group.

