Recruitment was originally closed on November 2021 after  $n = 92$  participants were randomized; however, based on the nature of the remote trial and participants dropping out after randomization, only 78 participants had baseline A1c data. Unexpectedly, 4/35 participants who completed the study in one group failed to obtain follow-up A1c and 2/33 in the other group failed to obtain follow-up A1c, resulting in complete data on  $n = 31$  per group. Reasons included the impact of COVID-19 and winter holidays coinciding with study conclusion or were not reported by the participants. A blinded analysis of the primary outcome by an independent statistician not involved in any other aspect of the trial was completed on January 16, 2022. After consultation with the statistician, the research team made the decision to re-open recruitment in order to obtain sufficient sample size based on the original calculations. Using an updated estimation of loss to follow up (62 complete data out of 92 randomized = 33%), we aimed to recruit an additional 10-12 participants in order to maximize the chances of having  $n = 34$  per group for final analyses.

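### The d = 0.4 to f = 0.2 conversion is wrong for a group-by-time interaction: 34 per group gives about 37% power at d = 0.4 (47% with cLDA), not 90%

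*Protocol*

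**What the plan says.** The Protocol (Sample size) derives d = 0.46 from an earlier breakfast trial and lowers it to 0.4 as a cautious choice. The test being powered is named in the sentence that begins "The total sample size necessary to detect a between-within interaction using repeated measures ANOVA with an effect size of". The value supplied there is 0.4, and the text equates it with f = 0.2; its phrase for this step is "which corresponds to an ANOVA effect size". The remaining inputs are a correlation of 0.5 between visits, power of 90% and alpha of 5%. The result is 68 completers, 34 in each arm. The inflation step opens "To account for a 20% dropout rate" and arrives at 41 in each arm. The SAP (Sample Size Considerations) repeats the same inputs and results.

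The SAP's January 2022 adjustment reports 92 randomised and 31 per group with complete HbA1c data. Recruitment was then re-opened on the basis of the same calculation, with 34 in each arm as the goal. The SAP puts the extra recruitment this way: "we aimed to recruit an additional 10-12 participants in order to maximize the chances of having".

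The Protocol (Blood samples) has HbA1c measured twice. The SAP's primary endpoint is the between-group comparison of change from baseline to 12 weeks, analysed by cLDA.

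**The concern.** Halving d to get f is correct when f describes the difference between two independent group means. Here f was entered for a group-by-time interaction with two visits. In that setting the same between-group difference is spread over four cells, and f is a quarter of d. If so, the trial was sized for an effect twice as large as the one it names, and the reduction from 0.46 to 0.4 gives no real conservatism.

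The Protocol's background section describes the trial as properly powered, and the 2022 decision to recruit again took 34 per group as the target. A non-significant result set beside a claimed 90% power at d = 0.4 could be taken as evidence against an effect of that size, which the trial cannot supply.

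**Working it through.** **Inputs.** From the Sample size sections of both documents: d = 0.4, f = 0.2, r = 0.5, power 90%, alpha 5%, N = 68. Two groups and two HbA1c measurements (m = 2). Sidedness is not stated; the ANOVA F test is equivalent to a two-sided test.

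**1. Reproduce the stated figure.** For the within-between interaction in G*Power's default form:

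λ = f² × N × m / (1 − r), with 1 and N − 2 degrees of freedom.

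- f = 0.2, N = 68: λ = 0.04 × 68 × 2 / 0.5 = 10.88, power 90.2%.
- f = 0.2, N = 66: power 89.3%.

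So 68 is the smallest even total that reaches 90%. The software was run correctly; the input is the problem.

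**2. What f should be.** Let δ be the between-group difference in change. After removing the group and time main effects, each of the four cells carries an interaction effect of +δ/4 or −δ/4. Hence f = δ / (4 × SD).

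- δ = 0.4 SD gives f = 0.1.
- f = 0.2 corresponds to δ = 0.8 SD.

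**3. Power at the stated effect.** f = 0.1, N = 68: λ = 0.01 × 68 × 2 / 0.5 = 2.72, power 36.9%. For 90% power, N = 266 (133 per group).

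**4. Check without the ANOVA formula.** SD of change = SD × √(2(1 − r)) = SD × √(2 × 0.5) = SD. The interaction test is therefore a two-sample t-test on change with d = 0.4 and 34 per group.

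- Noncentrality = 0.4 × √(34/2) = 1.649. Its square is 2.72, the same λ as in step 3, and power is again 36.9%.
- With d = 0.8 the same test gives 90.2%.
- Simulation of 40,000 trials gave 36.9% at 0.4 SD and 90.3% at 0.8 SD.

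**5. Planned analysis.** cLDA with two visits is approximated by follow-up adjusted for baseline. The residual SD is SD × √(1 − r²) = 0.866 SD, so the effective d is 0.4 / 0.866 = 0.462. Power with 34 per group is 46.7%. About 100 per group are needed for 90%.

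**6. Difference detectable with 90% power, 34 per group, r = 0.5.** 0.80 SD on change; 0.69 SD with cLDA.

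**7. Sensitivity, 34 per group, two-sided 5%.** Values of r other than 0.5 are assumptions, with d standardised by the single-visit SD.

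| d | r | Change score | cLDA (approx.) |
|---|---|---|---|
| 0.4 | 0.5 | 37% | 47% |
| 0.4 | 0.7 | 55% | 62% |
| 0.4 | 0.8 | 73% | 77% |
| 0.4 | 0.9 | 95% | 96% |
| 0.46 | 0.5 | 46% | 58% |

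A one-sided 5% test at d = 0.4, r = 0.5 gives 49.5% on change. With the 31 complete cases per group reported in January 2022, two-sided power is 34% (change) or 43% (cLDA).

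**8. Dropout.** 34 / (1 − 0.2) = 42.5, so 43 per group (86 in total). The stated 41 matches 34 × 1.2 = 40.8. With 20% loss, 41 × 0.8 = 32.8 completers, below 34. The loss that 41 can absorb is 1 − 34/41 = 17.1%.

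**The case against.** - **The 37% belongs to a test that will not be run.** True. The SAP plans cLDA, and its figure at the same inputs is about 47%. Both should be quoted. Neither is near 90%.
- **The documents call r = 0.5 conservative, so the true correlation may be higher.** If d is standardised by the single-visit SD, power rises with r and reaches 90% at about r = 0.87. That stands as a sensitivity. Neither document reports or argues for such a value, and the claim of 90% is made at r = 0.5.
- **The meaning of d is not shown.** The SAP places the 0.46% reduction within the big-breakfast group, and no SD is given. Reading d as the standardised between-group difference in change is therefore an assumption, though the natural one for the stated endpoint. Whether d uses the SD of change or the single-visit SD makes no difference at r = 0.5, because the two are equal.
- **Power for the clinical target in HbA1c units could be better.** Suppose the between-group difference were 0.46 percentage points. At r = 0.5, an assumed SD of 1.0 gives 46% (change) or 58% (cLDA), 0.8 gives 65% or 77%, and 0.7 gives 76% or 87%. This is fair, but it changes the effect size and does not repair the stated claim at d = 0.4.
- **The trial is finished and the dropout target is superseded.** The SAP says the study was completed by June 2022, and it has already replaced 20% loss with 33%. This limits the remedy to wording and makes the dropout error minor. The error does not bias the estimate or inflate type 1 error. The power statement is still wrong as written.

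**Conclusion.** The concern holds. At the documents' own d = 0.4, r = 0.5 and 34 per group, two-sided 5%, power is 36.9% for the interaction test that was powered and about 46.7% for the planned cLDA. At those inputs the trial is more likely to miss the named effect than to find it. The 90% figure applies to a difference in change twice as large as the one stated.

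The result rests on two things: d being the between-group difference in change in SD units, and r = 0.5 as specified. Only a correlation of about 0.87 or more, which the documents do not claim, would bring power at d = 0.4 to 90%. The dropout arithmetic is also wrong, by two per group, with little consequence.

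**What to change.** Add a dated correction to the sample-size sections of both documents, leaving the original calculation visible as the design record. Suggested wording:

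> With r = 0.5 and a two-sided 5% test, 34 completers per group give 90% power for a between-group difference in HbA1c change of 0.80 SD (0.69 SD with cLDA). Power for a difference of 0.4 SD is about 37% (47% with cLDA). A non-significant primary result will be interpreted from its confidence interval and not as absence of an effect of 0.4 SD.

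State how d is defined and which SD it uses. In one line, note that 41 per group allows for 17% loss and that 20% loss would have needed 43 per group (86 in total).

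The cost is wording and a less favourable power statement. No more participants are needed and the primary analysis does not change.

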## **SAMPLE SIZE CONSIDERATIONS**

We used a previous breakfast intervention in T2D along with our recently published one-day egg-based low-carbohydrate (LC) breakfast trial to calculate the sample size for this RCT. Rabinovitz et al  compared a “big breakfast” containing higher fat and protein providing 33% total daily energy to a small breakfast providing 12.5% daily energy over 3 months in a similar sample of participants with T2D using a similar parallel-group design. They reported an absolute reduction in HbA1c% of 0.46% in the big breakfast group. This is similar to the magnitude of change observed in a recent study by Nichols et al  who reported an average HbA1c reduction of 0.45% in response to metformin, the standard prescribed medication for people newly diagnosed with T2D. For this reason, it is reasonable to use the study published by Rabinovitz et al to estimate a clinically relevant effect size for our sample size calculation. A medium effect size (Cohen’s  $d = 0.46$ ) was calculated from the Rabinovitz study. In agreement, for our recent one-day study examining an egg-based LC breakfast (3), the effect size (Cohen’s  $d$ ) for improvements in CGM-derived glucose control variables (including AUC, iAUC, glycemic variability, and mean) ranged from  $d = 0.48-1.2$ .

Taking a conservative approach, we used an effect size of  $d = 0.4$  in the sample size calculation. The total sample size necessary to detect a between-within interaction using a repeated measures ANOVA with an effect size of  $d = 0.4$  (which corresponds to an ANOVA effect size  $f = 0.2$ ) with 90% power and 5% type 1 error with a conservative correlation among repeated measures of  $r = 0.5$  is 68 ( $n = 34$  per group, calculated using G\*Power v3.1.9.2). To account for a 20% dropout rate (2), we aimed to recruit a sample size of  $n = 41$  per group. These calculations were documented in the original grant application (Feb 2019), trial protocol (Dec 6, 2019), and SAP (Nov 17, 2021).

Adjustment as of 16th January 2022:

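### Recruiting 41 per group does not cover 20% dropout from the required 34 per group; it covers about 17% (minor, overtaken in practice)

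*Protocol*

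**What the plan says.** The protocol (Sample size) sizes the trial on an interaction test: "The total sample size necessary to detect a between-within interaction using repeated measures ANOVA". The inputs are d = 0.4, expressed as f = 0.2, "with 90% power and 5% type 1 error", and a correlation of 0.5 between repeated measures. The result is 68 in total, 34 per group. The dropout step follows at once: "To account for a 20% dropout rate [9] we will recruit a sample size of" 41 per group.

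The Research Method section carries this into a total of 82 and the two arms: "Eligible participants will be randomized to either the Low-carb High-fat breakfast (LCHF, n=41", with the same number for control.

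The SAP (Sample Size Considerations) repeats the calculation in the past tense: "To account for a 20% dropout rate (2), we aimed to recruit a sample size of" 41 per group. It then records an adjustment dated 16 January 2022. By then 92 had been randomized and 31 per group had complete data. Loss was re-estimated at 33%, and a further 10 to 12 participants were sought so as to reach 34 per group. Neither document gives the formula that turns 34 into 41.

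**The concern.** A dropout allowance should ensure that, after the assumed fraction is lost, the number needed for analysis remains. The lost fraction applies to those recruited, so the required number is divided by the retained fraction. Multiplying it by one plus the dropout rate always gives too few. Here the stated 41 agrees with multiplication and not with division.

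What is at stake is whether the sample size statement is true on its own terms. Under the plan's own 20% dropout, the stated recruitment does not give the stated number of completers, and so not quite the stated power. A report that takes its sample size paragraph from these documents would repeat the error.

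**Working it through.** **Inputs.** All but one come from the protocol's Sample size section: f = 0.2, two groups, r = 0.5, 5% type 1 error, 90% power, 34 per group required, 20% dropout, 41 per group recruited. The number of measurements is not stated there. I take m = 2, because HbA1c is measured at baseline and at 12 weeks.

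**Step 1: reproduce the 68.** For the within-between interaction, the noncentrality is lambda = f² x N x m/(1 - r), with 1 and N - 2 degrees of freedom.

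- N = 68: lambda = 0.04 x 68 x 2/0.5 = 10.88, power 0.9015. This is the smallest N that reaches 0.90, so the stated 68 is reproduced exactly.
- With m = 3 the answer would be 56, so m = 2 is the reading that fits.

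**Step 2: find the formula behind 41.**

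- Multiplying: 34 x 1.2 = 40.8, rounded up to 41.
- Dividing: 34/0.8 = 42.5, rounded up to 43 per group, or 86 in total.

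Only multiplication gives 41. That this was the method is an inference.

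**Step 3: what 41 per group delivers.**

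- Expected completers at 20% loss: 41 x 0.8 = 32.8 per group, 65.6 in total.
- Largest loss that still leaves 34: (41 - 34)/41 = 7/41 = 17.1%.
- For comparison, 43 x 0.8 = 34.4 per group.

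**Step 4: power at those numbers, same formula.**

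| Completers in total | lambda | Power |
|---|---|---|
| 65 | 10.40 | 0.888 |
| 66 | 10.56 | 0.893 |
| 68 | 10.88 | 0.9015 |

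The loss is about one percentage point.

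**Step 5: the January 2022 adjustment in the SAP.**

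- Retention: 62/92 = 0.674.
- Total after re-opening, if the aim was met: 92 + 10 = 102 to 92 + 12 = 104, or 51 to 52 per group.
- Expected completers: 102 x 62/92 = 68.7 to 104 x 62/92 = 70.1, against 68 needed.
- Dividing by retention: 68/0.674 = 100.9. Multiplying would have given about 68 x 1.33 = 90.4. The re-opened target fits division.

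**The case against.** The strongest reply is that the error had no practical effect. The trial randomized 92 before re-opening, already more than the 86 that correct inflation gives. At 20% loss, 92 x 0.8 = 73.6 would have completed. The shortfall to 31 per group arose because loss was about 33%, not because 41 was planned instead of 43. The re-opened target then put the expected number of completers at or above 68. All of this stands, and it limits the point to a misstatement in the text.

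A reader might infer that the SAP's target of 34 per group at re-opening carries the error forward. It does not: 34 is the completer requirement before any inflation, and the dropout formula never touches it.

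It can also be said that the SAP's mixed model keeps participants who have only a baseline or only a follow-up value, so counts of complete pairs slightly understate the data used. That is true. But the SAP itself counts complete data and treats 31 per group as short of 34, so completers are the right unit for checking this statement. I do not claim that the extra single values close the gap.

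Finally, the SAP passage is a record of what was planned. Replacing 41 by 43 there would misreport history. That objection is correct and shapes the fix.

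**Conclusion.** The statement is wrong as written and the error is minor. That 41 less 20% is 32.8 and not 34 needs no assumption about which formula was used. The recruitment figure is short by two per group, or four in total (82 against 86). The power cost is about one percentage point, 0.89 against 0.90, given the sponsor's f = 0.2 and r = 0.5 and two measurements.

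A reader might go further and conclude that the trial is materially underpowered because of this step, or that more participants are needed. The documents do not support that. The January 2022 adjustment aims for 102 to 104 in total and gives about 69 to 70 expected completers at the observed retention. This assumes that the extra recruitment was achieved and that retention stayed at 62/92; the SAP does not give the final count.

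The 89% figure holds only under the sponsor's inputs. Any doubt about the effect-size input is a separate issue and is not settled here.

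**What to change.** In the protocol (Sample size, and where the figure recurs in Research Method), state that 41 per group covers about 17% dropout, that 43 per group would be needed for 20%, and that power at 20% dropout is about 89% under the sponsor's own inputs.

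In the SAP (Sample Size Considerations), leave the historical target of 41 per group as recorded. Add one sentence saying the same and noting that the January 2022 adjustment superseded the target. Repeat that sentence in the final report.

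The cost is wording only: a slightly less favourable description of the planned sample, with no change to recruitment, data or analysis.
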